#### 16.8.2 External Audit

All Essential Documentation (i.e. eTMF of the Sponsor and/or ISF at the investigational site) will be made available for external auditors for formal Inspection if/when requested.

## 16.9 Publication and Dissemination Policy

## 16.9.1 Dissemination Policy

The Sponsor will own the raw data collected for this clinical study. Upon completion of the study, the Sponsor will be responsible for analysing the data, producing a Final Study Report and ensuring the results are accessible to the public. The Sponsor will dedicate a section of their website to the clinical study results. Study participants will be provided with the website address, so they are able to access the results if they so wish in due course. For transparency, the website will clearly state if the results are pending and the date when the Final Study Report is expected to be published. If any study participant contacts the site research team to enquire about the study results, they will be referred to the Sponsor website for information.

The Sponsor will also aim to publish the study results in appropriate journal/s. The CI will be encouraged to publish aspects of the analysed version of the study data, recognising the contribution of the study design team.

The Final Study Report will be made available within 1 year from the completion of the study, with the expectation that submission to journals for publication would be made in parallel.

There are no additional funding streams for this clinical study and therefore no additional review or publication rights to consider.

Whilst the full complement of essential trial documents will be made available to the relevant Regulatory Authorities, these will not be publicly accessible.

## 16.9.2 Authorship Policy

The Sponsor does not intend to employ professional writers to produce the Final Study Report. Those involved in the design, development and implementation of the clinical study will be recognised in any publications.

#### 17.0 INDEMNITY

The subjects that take part in this clinical trial will be covered by the Sponsor's insurance policy.

The insurance policy will cover:

1. Any potential legal liability of the Sponsor and/or Employers for harm to participants arising from the management of the clinical study.

[figure not shown]

- 2. Any potential payment of compensation in the event of harm to participants where no legal liability arises.
- 3. Any potential legal liability arising in relation to any equipment provided by the Sponsor for use in the study, such as loss, damage, maintenance responsibilities for the equipment itself, harm to participants or site staff arising from the use of the equipment.

In addition, the clinical site will ensure their NHS indemnity scheme covers any potential legal liability of the investigators/collaborators arising from harm to participants in the conduct of the clinical study, prior to commencing recruitment of participants into the study.

#### 18.0 DATA COLLECTION, HANDLING AND VERIFICATION

#### 18.1 Figure 2: Overview of Data Flow

#### 18.2 Source Documentation and Data Verification

The clinical site will confirm the location where all data will be recorded for the clinical study. This original documentation of data is referred to as source documentation. The clinical site will keep the source documentation secure and will provide it for review and verification by the study monitor as required. The data generated by purpleDx for the Breath Scan will be displayed on the phone screen then automatically submitted to the secure cloud storage. This will constitute the original source data for the purpleDx Breath Scan readings, which will be converted into a pdf document and returned to the

site for filing in the subject's medical record. The site team is required to transcribe the readings displayed on the screen at the time of measurement onto the visit paper record to serve as a backup in case an error occurs in the electronic process. If no pdf document is available, the handwritten visit record will constitute the source document. If any discrepancies are noted between the pdf document and the handwritten visit record, the Sponsor will be notified and asked to review the raw data to confirm correctness. If it is possible to provide the Pulse Scan measurements in a pdf document, this will also serve as the source document. However, if this is not possible, the handwritten visit record will constitute the source document.

## 18.3 Clinical Site Training and Initiation

The Sponsor will provide study-specific training to the site team at a Site Initiation Visit (SIV) to ensure the requirements of the protocol are fully understood and will be consistently complied with for all study subjects. The SIV may take place in person or via weblink and will include sufficient time to resolve all questions that may arise.

In addition, and before the clinical site can commence the recruitment of subjects into the clinical investigation, the site must provide all required documentation to the Sponsor as detailed in Appendix 13.

Upon receipt of the necessary documentation, the Sponsor will provide a formal letter of confirmation of site authorisation to begin the study to the local team. Recruitment of subjects into the clinical study can then begin at the site.

## 18.4 Retention of Source Documentation

To comply with the requirements of the regulators for marketing of new medical devices, the Essential Documentation for the clinical study must be retained by the site or Sponsor for at least 10 years following the end of the study or when the device was last placed on the market. If the paperwork is to be archived by CUH off site, the details of the location must be provided to the Sponsor in case access is required at any time.

#### 20.0 APPENDICES

## 20.1 Appendix 1: purpleDx Interaction Workflow

The diagram below illustrates the interaction and workflow between the CI/RN, subject and the investigational medical device (purpleDx app) to perform the measurement scans and collect results outlined for this protocol.

[figure not shown]

## 20.2 Appendix 2: Images of Subject Using purpleDx

The purpleDx app should be used with the subject sitting upright or reclining on a bed/trolley (with angle of incline recorded). For the trial purposes, the subject cannot lie completely flat (supine). The smartphone should be immobilised using a phone stand or by leaning it against a sturdy, static object.

[figure not shown]

# 20.2.1 Breath Scan (PEF, FEV1 and RR) with Phone Stand

# 20.2.2 Pulse Scan (HR) with Phone Stand

# 20.2.3 Pulse Scan (HR) with Phone Against a Static Object

[figure not shown]

## 20.3 Appendix 3: purpleDx Screenshots

## 20.3.1 Subject Input Screen

Upon logging into purpleDx, the Cl/RN or designee is taken to an initial screen where they must enter specific data required for the scans, as follows:

- Patient ID (Unique Subject Study Number)
- Age in years
- Height in cm
- Weight in kg
- Chest circumference in cm
- Sex at birth

## 20.3.2 Scan Selection Screen

This screen allows the subject to select which type of scan to perform.

[figure not shown]
## 20.3.3 Instructions Screen for Breath Scan (PEF, FEV₁ and RR)

When the subject clicks on 'Breath Scan' on the Scan Selection Screen, they will be taken to the step-by-step instructions on how to properly position the smartphone and position themselves, as well as how to perform the breathing manoeuvre to complete the Breath Scan. Once the subject is correctly positioned, the app will automatically begin the scan.

[figure not shown]

The subject should breathe 'normally' for the first 4 breaths, followed by a full breath out, then a deep breath in. When they then next breathe out, it should done as forcefully and quickly as possible. At the end of the exhale, the subject should hold their breath for 5 seconds before resuming breathing as 'normal'. This is shown in the graph below.

## 20.3.4 Recording Screens for Breath Scan (PEF, FEV₁ and RR)

[figure not shown]

The back arrow in the top lefthand corner of the screen can be used to prematurely stop the one-minute scan if something untoward happens and it is clear that an accurate and reliable scan will not be achieved e.g. if the subject sneezes or coughs.

# 20.3.5 Instructions Screen for Pulse Scan (HR)

[figure not shown]
Similarly, clicking 'Pulse Scan' takes the subject to step-by-step instructions for how to position themselves so that their face is within the oval shown on the screen. Once the subject is in the correct position, the scan begins automatically.

[figure not shown]

## 20.3.6 Recording Screens for Pulse Scan (HR)

The screenshots below show the screens presented to the subject during the Pulse Scan.

[figure not shown]

The back arrow in the top lefthand corner of the screen can be used to prematurely stop the one-minute scan if something untoward happens and it is clear that an accurate and reliable scan will not be achieved e.g. if the subject sneezes or coughs.

## 20.3.7 Results Screen for Breath Scan (PEF, FEV₁ and RR)

The three sets of results for PEF, FEV1 and RR will appear on the Results screen within 2 to 3 minutes of the measurements being taken, depending on the speed of the internet connection.

If any of the three sets of measurements have been unsuccessful and there are missing results, the CI/RN should ask the subject to repeat the Breath Scan. If there are any obvious reasons as to why the scan did not work, these will be noted by the CI/RN along with the need to perform a repeat scan. When the scan has been repeated, the results screen with be updated to include all successful measurements on the same screen.

A maximum of 3 retry Breath Scans should be attempted as needed to produce 3 results for each of the 3 parameters PEF, FEV1 and RR. If there are still missing data after 3 retry Breath Scans have been carried out, the missing results will be recorded as 'Not Available' (NA). The number of additional scans needed will be recorded.

Confirmation of the results for PEF, FEV1 and RR will subsequently be sent to the CI/RN as a PDF document for filing in the subject's medical notes to enable verification.

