For HR, the subject presses 'Pulse Scan' and follows the on-screen instructions to position their face to fit the oval shown on the screen. Once the face is correctly positioned, the app will automatically start the recording. A countdown of the sixty-second recording period will be displayed on the screen during the scan. The HR results will appear after each Pulse Scan has been performed.

Screenshots of the various app screens are shown in Appendix 2.

Although not done as part of this clinical protocol, data could potentially be collated over time as the patient performed sequential testing.

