The subject will use the purpleDx device to perform the Breath Scan to measure PEF, FEV1 and RR three times. Concurrently, the CI/RN or designee will observe the subject and count the number of breaths taken during each Breath Scan and will record the results on the source document. The CI/RN will use the standard Vitalograph spirometer equipment to obtain three sets of measurements for PEF and FEV1. The subject will then use the Pulse Scan on the new device to obtain three HR readings. A standard pulse oximeter will be used concurrently to obtain three HR results. Thus, three sets of results will be produced for PEF, FEV1, RR and HR by both the standard means and by the investigational equipment. Appendices 1 and 2 provide a detailed overview of the process and the app screenshots. For details of the equipment being used in the study, see Appendix 6. The purpleDx results will be displayed on the smartphone screen. The CI/RN or designee will copy the results from the new device and the standard equipment onto the subject's paper visit records to act as the source document for the parameter values. A PDF file will subsequently be emailed to the CI/RN or designated member of the clinical study team to verify the handwritten source document results from the purpleDx Breath Scan.

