## 14.7.2 Specific Strategies

## ● For PEF and FEV₁:

- o If a patient is unable to provide three acceptable blows, the best available single reading will be used (if at least one acceptable effort exists).
- o If no valid readings can be obtained from either the new device or reference method, that data point will be recorded as **missing**.

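### For PEF (primary endpoint) and FEV1, the protocol does not protect the spirometry reference from knowledge of the purpleDx result

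*Protocol*

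**What the plan says.** **Who does what.** Section 11.0 has the subject perform three Breath Scans and then describes the reference: "The CI/RN will use the standard Vitalograph spirometer equipment to obtain three sets of measurements". It adds that "The purpleDx results will be displayed on the smartphone screen" and that "The CI/RN or designee will copy the results from the new device and the standard equipment onto the subject's paper visit records". One role, the CI/RN or designee, therefore handles both methods and a single paper record.

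**When the device values become visible.** Section 20.3.7 says that the Breath Scan values "will appear on the Results screen within 2 to 3 minutes of the measurements being taken". If any are missing, "the CI/RN should ask the subject to repeat the Breath Scan", so the operator has to inspect that screen during the visit. Section 18.2 also requires the site team to write down the displayed readings at the time of measurement.

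**How the reference value is formed.** Section 14.2 takes the best effort of three for PEF and FEV1. Section 14.7.2 adds: "If a patient is unable to provide three acceptable blows, the best available single reading will be used". The visible text does not state what makes a blow acceptable.

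**Heart rate.** "A standard pulse oximeter will be used concurrently to obtain three HR results" (section 11.0), and "The HR results will appear after each Pulse Scan has been performed" (section 7.2).

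**The concern.** An agreement study can be interpreted only if neither reading influences the other. Forced spirometry depends on effort. The operator decides how hard to coach, whether a blow counts and whether to ask for another. An operator who already knows the purpleDx PEF may make those decisions with that figure in mind, without intending to. A subject who has seen it may also aim for it.

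PEF agreement is the sole primary endpoint and is meant to support a marketing application. If the reference moves towards the device, the within-20% proportion, the Bland-Altman limits and the ICC all look better together. None of the planned analyses could detect or undo this, so it has to be prevented at the visit.

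**Working it through.** **1. The plan's own figure.** Section 14.4.1 uses p0 = 0.80, p1 = 0.90, two-sided alpha 0.05 and 90% power:

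n = (1.96 × 0.4 + 1.2816 × 0.3)² / 0.1² = (0.784 + 0.3845)² / 0.01 = 136.5, rounded up to 137.

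This reproduces the stated 137. The concern does not change it.

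**2. What a positive result needs.** Section 14.3.2 requires a lower Wilson 95% bound of at least 0.80. The bound is

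[p + z²/2n − z√(p(1−p)/n + z²/4n²)] / (1 + z²/n), with z = 1.96.

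For the 150 analysable subjects aimed at in section 14.4.1:
- 129/150 = 0.860 gives 0.795, which fails.
- 130/150 = 0.867 gives 0.803, which passes.

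So 130 successes are needed. At n = 137 the number is 119.

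**3. Sensitivity of that rule.** Exact binomial chance of a positive result:

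| Proportion within ±20% | n = 150 (≥130) | n = 137 (≥119) |
|---|---|---|
| 0.78 | 0.5% | 0.6% |
| 0.80 | 2.2% | 2.4% |
| 0.82 | 8.0% | 8.2% |
| 0.84 | 22.1% | 21.6% |
| 0.85 | 33.2% | 32.0% |
| 0.90 | 92.8% | 91.0% |

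At n = 150 a lift of 2 points is 0.02 × 150 = 3 subjects, and 4 points is 6 subjects. From a true 0.80, these lifts take the chance of a positive result from 2.2% to 8.0% and 22.1%. From a true 0.78, a 4-point lift (to 0.82) takes it from 0.5% to 8.0%.

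**4. Direction.** Take success as two-sided, in line with the ±20% in section 14.3.2: 0.8G ≤ P ≤ 1.2G, where P is the device value and G the spirometry value. Because G is a best effort, extra coaching can only raise it. A higher G brings in subjects with P > 1.2G and pushes subjects with P < 0.8G further out. Net inflation therefore needs coaching that responds to the device value, with more effort sought when the device reads high. That selectivity is what seeing the screen makes possible.

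**5. Illustration, on assumptions not in the documents.** Assume a blow-to-blow coefficient of variation of 3% to 8%, and a device spread set so that 80% fall within ±20% when the operator does not know the device value. If one to three extra blows are sought only when the device reads more than 20% high, the simulated proportion becomes 0.81 to 0.84. The chance of a positive result at n = 150 becomes 4% to 24%. This shows that a lift of a few points is possible, not that it will happen.

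**The case against.** **The order is not established.** In section 11.0 the sentence on spirometry has no sequence word, and Figure 1 and the Appendix 1 workflow diagram are not shown. If spirometry is done first, or is finished within the processing time, the route closes. This stands as a caveat. It does not remove the point, because no visible rule fixes the order or requires the reference to be written first.

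**One role need not be one person.** The text says CI/RN or designee, so two people could share the work. That is true, but nothing requires it.

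**The size is assumed.** The binomial figures would describe a shift of a few points from any cause. They matter most near the 0.80 threshold; at the planned 0.90 the study would pass about 93% of the time anyway. This stands.

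**Stronger readings that the documents do not support:**
- *All four references are affected.* Respiratory rate is not, in the main. Breaths are counted during each Breath Scan, and the device rate appears only after all three scans have been analysed. Only counts during retry scans could follow a displayed value. Nor would one miscounted breath necessarily decide an outcome, since section 14.2 uses the average of three.
- *Heart rate is equally exposed.* The oximeter is an instrument readout taken during the scan, and the matching app value appears only afterwards. At most, the first app value is known before the second and third oximeter readings.
- *The bias always favours agreement.* Step 4 shows that it need not.

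**Conclusion.** The point holds for PEF and FEV1, as an unprotected reference rather than a demonstrated bias. The visible text has the CI/RN role view and transcribe the purpleDx values during the visit and also obtain a reference that depends on effort and judgement. It contains no safeguard between the two.

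Any influence would tend to favour agreement, but its size is unknown. If the true proportion were 0.80, an assumed lift of 2 to 4 points would raise the chance of a positive primary result at n = 150 from 2.2% to between 8.0% and 22.1%. This rests on the assumed lift and on the narrated order, in which spirometry follows the scans.

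For heart rate there is only a minor note, and for respiratory rate no finding. The PEF and FEV1 safeguard should be in place before the first subject, because the problem cannot be repaired after data collection.

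**What to change.** **Section 11.0, with Appendix 1 and section 18.2 aligned.** Require that the spirometry blows are completed, accepted and written down before the purpleDx Results screen is opened to operator or subject. The 2 to 3 minutes of processing can be used for this; if spirometry takes longer, the screen stays unopened until the values are recorded. Transcription of the device values under section 18.2 then follows. Any repeat Breath Scans are done after spirometry and flagged in the record.

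**Minor addition.** Write down each concurrent oximeter reading before the app heart rate for that scan is viewed.

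**Cost.** Protocol and training wording only. The sample size and the app are unchanged and no extra visit is needed. The Breath Scan values are uploaded automatically and returned as a PDF, so nothing is lost by opening the screen later.

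**Downside.** Repeat Breath Scans would follow spirometry and be supervised by someone who knows the spirometry result. The flag lets the primary proportion also be shown without those subjects.

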## 20.3.8 Results Screen for Pulse Scan (HR)

[figure not shown]
The screenshots below display the result for HR at the end of each Pulse Scan.

Following successful measurement of HR

[figure not shown]
## Following an unsuccessful measurement of HR

If the scan has been unsuccessful, the subject can perform the scan again. The protocol requires 3 readings for HR. A maximum of 3 additional retry pulse scans should be attempted if needed to produce the 3 readings. If 3 HR results are still not produced by the end of performing 3 pulse scans, the missing results will be recorded as 'Not Available' (NA).

# 20.3.9 Profile Screen and Change Patient Button

## 20.4 Appendix 4: The Fitzpatrick Scale

Type I	Type II	Type III	Type IV	Type V	Type VI
White skin. Always burns, never tans.	Fair skin. Always burns, tans with difficulty.	Average skin color. Sometimes mild burn, tan about average.	Light-brown skin. Rarely burns. Tans easily.	Brown skin. Never burns. Tans very easily.	Black skin. Heavily pigmented. Never burns, tans very easily.

The device Skin Colour Tester manufactured by PMUBEAUTY (Reference B0C772RJ33) will be used by the research nurse to assess each subject's skin tone according to the Fitzpatrick Scale. This device will be provided by the Sponsor to the clinical site and approved for use by their medical engineering team prior to study commencement.

# 20.5 Appendix 5: Determination of Pregnancy for Women Of Child-Bearing Potential

For the purposes of the inclusion/exclusion criteria for this clinical trial, it is not necessary to use a pregnancy test to exclude pregnancy in Women of Child-Bearing Potential (WOCBP). Since the app simply performs a non-invasive scan using the phone's camera functionality there is no risk to any subject or potential offspring. The CI/RN or designee will ask the subject if there is any possibility that they might be pregnant. If the subject thinks they may be pregnant they will be excluded from participation in the study. This is a precautionary measure as it may have a bearing on the ability of the app to produce reliable results (particularly in the second and third trimesters when lung capacity may be impinged by the developing offspring) and pregnant women have not been included in the verification and validation processes on the apps used during the developmental process of purpleDx.

## 20.6 Appendix 6: Equipment Used in the Clinical Study

- iPhone version 15 with purpleDx app version 6.0.0 downloaded ready for use
- Vitalograph Pneumotrac Model 6800 with Spirotrac® 6 Software Model 7000 serial number PV11145 for standard measurement of PEF and FEV1
- Nonin WristOx2 pulse oximeter for standard measurement of HR
- RSO PRO ILM 1337 Light Meter, +/- 3% +/-5 Digits
- Fitzpatrick skin tone meter: Skin Colour Tester manufactured by PMUBEAUTY (Reference B0C772RJ33)
- Reference fiducial markers to fix to subject's hands to aid visual tracking to enable purpleDx to measure PEF, FEV₁ and RR.

The Vitalograph spirometer, Nonin pulse oximeter, light meter and Fitzpatrick skin tone meter will be provided by the Sponsor and must be approved as safe for use by the site's medical engineering team prior to study commencement. The reference fiducial markers will also be provided by the Sponsor for use in the study.

